## Trial population

Eligibility criteria are stated in the study protocol version 2.0 (January 7th 2022). The criteria have been updated with minor changes from version 1.0 (December 21st 2021). Primarily one additional exclusion criterion was added “planned or expected admission >10 days for other condition than heart failure”, and two exclusion criteria were clarified: “Known or suspected malignant disease” was changed to “clinically indicated diagnostic thoracentesis (e.g. suspected malignant aetiology)” and “eGFR<15ml/min/1.73m^2 or acute renal failure” was changed to “eGFR<15ml/min/1.73m^2 or dialysis treatment”. Eleven participants were included under the criteria in protocol version 1.0. The impact of the changes in eligibility criteria is

believed to be minor, and we do not see the need for stratification of the population based on whether they were included before or after the implementation of protocol version 2.0.

The following will be reported.

- The number of patients screened for eligibility with an explanation for the exclusion
- The number of patients randomised
- The number of participants allocated to each group.
- The number of participants that followed the treatment strategy according to the protocol (patients in the intervention arm being referred to upfront thoracentesis by the treating physician (scheduling when the thoracentesis will be performed) and patients in the control arm who are not referred to thoracentesis within five days after randomisation)
- The number of participants that received the planned treatment according to the allocated treatment strategy (thoracentesis performed on participants in the interventional group and thoracentesis not performed on participants in the control group).
- The number of participants in the intervention group that did not have thoracentesis performed and the number of participants in the control group that had thoracentesis.
- The number of participants that withdrew from the trial or were lost to follow-up with an explanation. The level of consent withdrawal will be reported (“consent to continued data collection and questionnaire follow-up”, “consent to continued data collection but no questionnaire follow-up”, “complete – no questionnaire follow-up or data collection”)
- The number of participants analysed for the primary outcome according to the intention-to-treat principle.

An overview of the trial population will be provided in a CONSORT flow diagram (presented as Figure 1 in the final publication)

## Statistical methods

### Analysis datasets

The primary analysis will be on the **full analysis dataset**, including all participants from whom written informed consent is obtained and randomised. Subjects will be analysed according to their allocated treatment group according to the intention-to-treat principle.

Exploratory analyses will be performed on the per-protocol and the as-treated datasets as defined below. The **per-protocol dataset** includes participants that followed the treatment strategy according to the

protocol (patients in the intervention arm being referred to upfront thoracentesis by the treating physician (scheduling when the thoracentesis will be performed) and patients in the control arm who are not referred to thoracentesis within five days after randomisation). The **as-treated dataset** is defined as participants who received the planned treatment according to the allocated treatment strategy (thoracentesis performed on participants in the interventional group and thoracentesis not performed on participants in the control group).

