## Adherence and protocol deviations and Randomization errors

The intervention and comparator in this pragmatic trial are two treatment strategies: referral to up-front thoracentesis in addition to pharmacological therapy compared with pharmacological therapy alone.

Compliance with the protocol is defined as the participant in the intervention arm being referred to upfront thoracentesis by the treating physician (scheduling when the thoracentesis will be performed). There is the possibility that the physician performing the procedure does not find enough pleural fluid to safely perform the thoracentesis. This case will not be considered a violation of the protocol. In the control group, participants receiving pharmacological treatment alone for five days after randomisation are considered compliant with the protocol.

Major protocol deviation is defined as patients randomised despite violating eligibility criteria. This is considered a randomisation error. Such cases will remain in the trial and have data collected. The ineligible participant will be included in the full analysis dataset because it is our perception that exclusions cannot be made in an objective and unbiased manner due to the unblinded nature of the trial, with a risk of introducing bias post-randomization [8]. The allocated treatment strategy is stopped if the reason for ineligibility means that commencing or continuing treatment is inappropriate or potentially unsafe (e.g. participants randomised despite an indication for diagnostic thoracentesis must be referred to thoracentesis; participants randomised despite a spontaneous bleeding disorder and therefore cannot undergo thoracentesis). Such cases will be analysed according to the allocated treatment arm in accordance with the intention-to-treat principle.

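### The per-protocol set conditions on referral alone, so a randomisation error that decides referral can be kept in one arm and dropped from the other

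*SAP*

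**What the plan says.** Under Adherence and protocol deviations and Randomization errors, the SAP gives a single definition: "Major protocol deviation is defined as patients randomised despite violating eligibility criteria". On what happens to such a participant it says "The ineligible participant will be included in the full analysis dataset", because "exclusions cannot be made in an objective and unbiased manner due to the unblinded nature of the trial". The allocated strategy is stopped where ineligibility makes it inappropriate or unsafe. Two examples follow: "participants randomised despite an indication for diagnostic thoracentesis must be referred to thoracentesis", and "participants randomised despite a spontaneous bleeding disorder and therefore cannot undergo thoracentesis". Nothing is said about where these participants stand in the per-protocol set.

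Analysis datasets defines that set by referral only. The intervention half, up to the point where the control half begins, is "patients in the intervention arm being referred to upfront thoracentesis by the treating physician (scheduling when the thoracentesis will be performed) and patients in". Controls qualify on a condition of their own, worded as "patients in the control arm who are not referred to thoracentesis within five days after randomisation". There is no eligibility condition. The Trial population section uses the same definition for one of the participant counts to be reported. The per-protocol analysis is labelled exploratory, and the main analysis of the primary outcome also runs on this set for exploratory purposes.

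**The concern.** A per-protocol set should apply one rule to both arms. Here the criterion is the referral decision, and for some randomisation errors that decision follows from a fact that existed before randomisation. Allocation then determines whether two participants with the same violation are both analysed. The set therefore selects on a baseline characteristic, possibly a prognostic one, differently by arm.

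A second, smaller consequence concerns reporting. A participant with the plan's only major protocol deviation can be counted as having followed the strategy according to the protocol, and nothing in the reported count would show it.

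At stake is how far the exploratory per-protocol estimate can be read as a check on the intention-to-treat result.

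**Working it through.** **Step 1. Apply the inclusion rule to each kind of violation, arm by arm.**

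| Violation | Intervention arm | Control arm |
|---|---|---|
| Diagnostic indication (SAP example: has to be referred) | Referred, so kept | Dropped if referred within five days; kept if referred later or if the violation is not recognised |
| Spontaneous bleeding disorder (SAP example: cannot have the procedure) | Dropped if the error is found before scheduling; kept if already referred, since compliance means referral and not performance | Not referred, so kept |
| Violation with no bearing on referral | Kept if referred as allocated | Kept if not referred, as allocated |

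The first two rows can differ between arms, and they differ in opposite directions. The third row does not differ by reason of the violation.

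**Step 2. Arm size.** Inputs from Sample Size and Statistical principles: difference 3 days, SD 5 days, two-sided alpha 0.05, power 90%. A two-sample t-test needs 59.35, so 60 per arm and 120 in total. The stated 126 is reproduced by 120 × 1.05 = 126. The 5% allowance is my reading, since the SAP states 5% in-hospital mortality but no inflation step. With 1:1 allocation, 126 / 2 = 63 per arm.

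**Step 3. Design value on the planned scale.** The planned analysis is of the Mann-Whitney parameter, not of a difference in means. Under the normal design assumptions:

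θ = Φ(3 / (5 × √2)) = Φ(0.424) = 0.664, which is 0.164 above the null of 0.5.

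**Step 4. Bound on the shift.** Assume that m participants of the first type are kept among 63 in the intervention arm, that their counterparts are dropped from control, and that all m rank worst. Their pairwise contribution falls from θ to 0:

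fall in θ = (m / 63) × 0.664

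- m = 1: 0.664 / 63 = 0.011, or about 6% of 0.164
- m = 3: 3 × 0.664 / 63 = 0.032, or about 19% of 0.164

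With no treatment effect (θ = 0.5) the fall is (m / 63) × 0.5, that is 0.008 for m = 1 and 0.024 for m = 3.

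For the second type, assume that m participants are kept in control and rank worst. Their contribution rises from θ to 1:

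rise in θ = (m / 63) × (1 − 0.664)

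- m = 1: 0.336 / 63 = 0.005
- m = 3: 3 × 0.336 / 63 = 0.016

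The values m = 1 to 3 and the worst-rank placement are assumptions. The SAP gives neither a rate of randomisation errors nor the outcomes of such participants.

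**The case against.** The best defence is that the plan is coherent on its own terms. It uses per-protocol to mean that the strategy was followed, treats randomisation errors as a separate matter, and never says that the set excludes them. That is right as far as it goes: the sections do not flatly contradict each other, and the point does not depend on a conventional definition that the plan did not adopt. What remains is that the referral rule removes some randomisation errors from one arm only.

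A second defence is that the SAP's reason for not excluding ineligible participants, the open-label design, applies to any such exclusion. The SAP attaches that reason to the full analysis dataset, and it cannot support a rule that already excludes some of these participants by arm. It does bear on the remedy. A work-up before a procedure may uncover a pre-existing disorder more often in the intervention arm, and dating the evidence before randomisation reduces that risk without removing it.

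Third, Background and rationale uses thoracentesis as shorthand for the therapeutic procedure, so it is arguable whether a purely diagnostic referral counts. The wording of the SAP's own example favours counting it, but the plan should make this clear.

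Fourth, any adherence-based set selects differently by arm. Eligible controls who worsen and are referred within five days are also dropped, and no eligibility condition changes that. This stands.

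**Conclusion.** The point holds in a limited form and is a cheap improvement. The per-protocol definition ignores the plan's only major protocol deviation. Where the violation decides referral, the same baseline violation can be kept in one arm and dropped from the other. The size is unknown. Under the assumptions shown, retention of the first type lowers the Mann-Whitney parameter by at most about 0.01 to 0.03.

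A reader might infer three stronger things that the SAP does not support:

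- **That ineligible participants in general are handled differently by arm.** Only violations that decide referral are, and then only with the timing shown in the table.
- **That the estimate is biased in a known direction.** The two examples push in opposite directions if both kinds of participant do worse than the rest, and nothing indicates which is more common.
- **That the bias could approach the 3-day design difference.** With m participants whose outcomes are g days worse, the shift in means is m × g / 63. Then 1 × 20 / 63 = 0.3 day and 3 × 40 / 63 = 1.9 days. But the planned analysis is rank-based, and both m and g are assumed.

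The primary intention-to-treat analysis is not touched.

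**What to change.** Change the definition under Analysis datasets, and the matching count under Trial population, so that the per-protocol set comprises participants without a major protocol deviation who also followed the allocated strategy. State that eligibility is judged:

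- by the same rule in both arms;
- from data dated at or before randomisation;
- against the protocol version in force at entry, since eleven participants entered under version 1.0 and the criterion on malignancy and diagnostic thoracentesis was reworded afterwards;
- without reference to allocation or outcome.

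Leave the full analysis dataset as written.

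The cost is about one sentence in the SAP and a few fewer participants in an exploratory analysis. Some risk remains that pre-existing violations are detected more often in one arm of an open-label trial. Reporting the number of major protocol deviations by arm and noting this as a limitation would let readers judge it.

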### Statistical principles

All outcomes are tested for superiority. A two-sided p-value  $<0.05$  is considered statistically significant, and a 95% confidence interval (CI) is reported for all effect estimates. No multiplicity adjustment will be applied.

### Timing of final analysis

All outcomes are analysed collectively after the 90-day follow-up of the last patient when data collection is completed.

### Baseline characteristics

Baseline patient characteristics and demographics will be reported for each group (Table 1 in the final publication).

Table 1: Baseline characteristics

Variable	Data type
Demographics	
Age (years)	Continuous
Sex (female) %(n)	Categorical
Race (white)	Categorical
Included at specialised referral centre %(n)	Categorical
Symptoms and physical examination	
Height (cm)	Continuous
Weight (kg)	Continuous
BMI (kg/m  )	Continuous
Rales %(n)	Categorical
Peripheral oedema %(n)	Categorical
Orthopnoea %(n)	Categorical
Ascites %(n)	Categorical

NYHA class %(n)	Categorical, ordinal
II	
III	
IV	
Fatigue %(n)	Categorical
The CSHA clinical frailty scale score [9,10]	Categorical, ordinal
Score<4 = frail %(n)	
Score>4 = not frail %(n)	
Heart failure characteristics	
LVEF (%)	Continuous
Time since HF diagnosis (months)	Continuous
New-onset HF %(n)	Categorical
Ischemic aetiology %(n)	Categorical
Medical history	
Cardiovascular comorbidities %(n)	Categorical
Atrial fibrillation	
Hypertension	
Comorbidities %(n)	Categorical
COPD	
Diabetes	
CKD	
Liver disease	
Smoking (former or active) %(n)	Categorical
Alcohol over 7 /14 units pr. week (woman/men) %(n)	Categorical
Laboratory values	
Haemoglobin mmol/L	Continuous
Sodium mmol/L	Continuous
Potassium mmol/L	Continuous
Creatinine micromole/L	Continuous
eGFR (mL/min/1.73m  )	Continuous
NT-proBNP (pmol/L)	Continuous
Albumin g/L	Continuous

Troponin T/I above the upper reference limit %(n)	Categorical
C reactive protein mg/L	Continuous
Treatment	
ACEi/ARB/ARNI %(n)	Categorical
Beta-blockers %(n)	Categorical
MRA %(n)	Categorical
SGLT2i %(n)	Categorical
Home loop diuretics %(n)	Categorical
Home loop diuretics dose (furosemide-equivalent dose, mg daily)	Continuous
Anticoagulant therapy %(n)	Categorical
VKA	
DOAC	
LMWH	
ICD %(n)	Categorical
CRT %(n)	Categorical

#### Statistical method for comparison of baseline characteristics

For descriptive statistics, normally distributed continuous variables will be reported as mean  $\pm$  standard deviation (SD), skewed distributed variables as median and interquartile range (IQR) and categorical variables as numbers (n) and percentages (%).

#### Outcome definitions and timing of outcome assessment

A detailed standard operating procedure (SOP ver. 2.0 TAP-IT data quality, collection, and definition version 28.07.22) for data collection has been prepared (key definitions summarised below)

Outcome	Type	Assessment time
Primary outcome		
Number of days alive outside hospital during the 90 days following randomisation.  Definition: A readmission is defined as admission to any department in the hospital due to any cause lasting over 24 hours or a change in calendar date.	Count, days	90 days after randomisation.
Secondary outcomes		

Number of days alive and not hospitalised due to heart failure during the 90 days following randomisation.  Definition: Readmissions meeting the above-mentioned criteria and related to heart failure based on the definition provided by The American Heart Association [11]	Count, days	90 days after randomisation.
Duration of index admission  Definition: The start date for hospitalisation in any department. The Department is registered, and the patients can be transferred between departments and hospitals (e.g. to specialised heart centres) during admission. The end of admission is defined as when the patient is discharged, either to their home facility or to care in the primary sector (nursing home, rehabilitation centre)	Count, days	From randomisation until the date of discharge from the hospital.
Changes from baseline in weight during admission  - Weight obtained within 24 hours from randomisation and discharge.	Continuous, kg	From randomisation until the date of discharge from the hospital.
Change from baseline in dosage of diuretics during admission  - Daily dose at discharge minus daily dose at baseline (both within 24 hours) - Maximum daily dose during admission minus daily dose at baseline (within 24 hours)	Furosemide-equivalent dose, Mg	From randomisation until the date of discharge from the hospital.
Time to death	Time to event, Days	90 days after randomisation.
Time to first readmission or death  Definition: A readmission is defined as admission to any department in the hospital due to any cause lasting over 24 hours or a change in calendar date.	Time to event, Day	90 days after randomisation.

Number of complications to interventional thoracentesis:  - Pneumothorax. - Intrapleural bleeding (haemothorax) - Infection requiring antibiotics (empyema) - Pain/discomfort with the need for analgesics - Organ laceration - Re-expansion pulmonary oedema. - Thromboembolic events within 30 days from discontinued anticoagulation therapy (deep vein thrombosis, pulmonary embolism, ischemic stroke, transient ischemic attack, systemic embolism, myocardial infarction)	Count	From randomisation until the date of discharge from the hospital.
Number of complications during the index admission  - Delirium requiring pharmacological therapy - Fall - Nosocomial infections like pneumonia, urine catheter-related infection, and central venous catheter-related infections requiring a change of the catheter and antibiotic treatment.	Count	From randomisation until the date of discharge from the hospital.
Kansas City Cardiomyopathy Questionnaire score (KCCQ-23)	Scores from 0-100.  100 representing the best outcome.	14 days after discharge from index admission and 90 days after randomisation
Satisfaction with hospital stay - Selected questions from the questionnaire "Questions about your admission" from the annual Danish National Survey of Patient Experiences"	Likert scale from 1-5. 5 represents the best outcome.	14 days after discharge from index admission

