#### Secondary objectives

To determine the effectiveness of a strategy of referral to upfront thoracentesis in addition to pharmacological therapy compared with pharmacological therapy alone on admission duration, dose of

diuretics, weight loss, mortality, complications, and patient-reported outcomes such as patient satisfaction and quality of life.

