### Sample Size

For estimation of sample size, we assumed a t-test of superiority and found a total of 126 participants required to detect a difference of three days in the primary endpoint with an  $\alpha$  of 0.05 and a power of 90%. This assumes, that participants assigned to a strategy with referral to up-front thoracentesis in addition to pharmacological therapy will have 85 days alive and not hospitalised during the 90 days after randomisation, while participants assigned to pharmacological therapy alone will have 82 days, with a shared standard deviation of 5 days, and in-hospital mortality of 5% in both groups [5–7]. For analysis of the primary endpoint, we will assess the Mann-Whitney parameter for days alive without hospitalisation during the 90 days following randomisation, using the Wilcoxon-Mann-Whitney-test [30]. The loss of power with the Wilcoxon rank sum test compared to the t-test is often limited if distributions are normal, and when normality is violated, the Wilcoxon rank sum test can be three or four times more powerful than the independent samples t-test [31,32]. The power of 90% will allow for a possible small loss of power from using the Wilcoxon-Mann-Whitney test.

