## Primary outcome definition

Number of days alive outside of the hospital during the 90 days following randomisation. The outcome is countable with a minimum value of 0 and a maximum of 90. In case of death before the end of follow-up, the participant will be assigned the number of days they were outside of the hospital until death occurred. If the participant dies during the index admission, they will be assigned 0 days alive and outside of the hospital (Auriemma et al., 2021; Granholm et al., 2023). We anticipate 95% of participants to be discharged from the hospital [5–7] and based on limited previous observation data in patients with heart failure-related pleural effusion necessitating thoracentesis, we anticipated 78-91% of participants to survive 30 days after hospitalisation [1,2].

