## Missing data for the secondary outcome

The extent of missing outcome data will be reported and discussed. Missing data from questionnaires on quality of life and patient satisfaction are anticipated and, in some cases due to the participants being deceased. The number and percentages of participants that completed questionnaire follow-up at 14 days and 90 days will be reported. For participants who did not complete the questionnaire during follow-up, an explanation will be provided if available. If an entire questionnaire is missing, we assume that this could be due to deteriorating health or death and the data is therefore missing not at random (MNAR) [15]. The main analysis will be as observed, and sensitivity analysis will be conducted for the best-worst and the worst-best case scenario. Patients who have died will be assigned the worst score (0), and patients who are alive and have not responded despite efforts to collect data (electronic reminders and telephone contact) are assumed to be of very poor to poor health and assigned the worst score (0). Missing data from

questionnaires on satisfaction with hospital stay (Likert scale 1-5, 5 representing highest satisfaction) follows the same assumption as KCCQ with data MNAR. However, it is not assumed that patients with poor health status or who die during follow-up necessary were dissatisfied with their treatment. Therefore, simple mean imputation will be used.

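### Index stay has two start points in one table row and no rule for in-hospital deaths, so the same data can give different results; weight change is also compared without baseline adjustment, at a small loss of precision (minor)

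*SAP*

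**What the plan says.** All references are to the SAP.

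- **Start of stay.** In Outcome definitions and timing of outcome assessment, the definition cell for index admission begins with "The start date for hospitalisation in any department". The assessment-time cell of that row says "From randomisation until the date of discharge from the hospital".
- **End of stay.** "The end of admission is defined as when the patient is discharged", to home or to primary-sector care. Death is not mentioned.
- **Expected deaths.** Sample Size assumes "in-hospital mortality of 5% in both groups". Primary outcome definition says "We anticipate 95% of participants to be discharged from the hospital".
- **Death rule.** For the primary outcome, "If the participant dies during the index admission, they will be assigned 0 days alive and outside of the hospital". Analyses of Secondary Outcomes carries the primary approach over only to days alive and not hospitalised for heart failure.
- **Missing data.** Missing data for the secondary outcome says "The main analysis will be as observed", within text about questionnaires.
- **Weight.** The outcome is the change from randomisation to discharge. Analyses of Secondary Outcomes compares continuous outcomes by t-test or Wilcoxon-Mann-Whitney test and names adjustment only for time-to-event outcomes.

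**The concern.** Admission duration is the first outcome named in Secondary objectives ("pharmacological therapy alone on admission duration, dose of"). Two analysts following the SAP could compute different stays from the same data.

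The start points differ for anyone randomised after the day of admission. The death gap matters more. If a death counts as the end of a stay, an early death looks like a quick recovery, and an arm with more deaths looks shorter. If deaths are left out, the comparison is conditional on surviving to discharge. The trial is open-label and applies no multiplicity adjustment, so a rule settled after the data are seen leaves an avoidable choice between results. Participants who die in hospital also have no discharge weight or discharge diuretic dose.

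The weight point is separate and smaller. A comparison of changes that ignores the baseline value is valid, but usually less precise than one that uses it.

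**Working it through.** **The plan's own figure.** A difference of 3 days with SD 5 is a standardised effect of 0.6. A two-sided t-test at 0.05 with 90% power needs 59.35, so 60 per arm and 120 in total. Then 120 × 1.05 = 126 (and 120/0.95 = 126.3). The stated 126 reproduces if the 5% mortality is read as an inflation. That is an inference, as the SAP shows no formula. Nothing below changes it.

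**Number of deaths.** 126 × 0.05 = 6.3 expected, or 3.15 per arm. The chance of at least one in a given arm is 1 − 0.95^63 = 0.96. For two independent Binomial(63, 0.05) counts, the arms differ by 0 or 1 in 47% of trials, by 2 or more in 53%, and by 4 or more in 15%.

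**How far a death rule can move the result.** Take 63 per arm, equal stays among survivors, and a v b deaths. The Mann-Whitney parameter is the chance that a participant in the arm with a deaths has the longer stay.

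- Deaths excluded: 0.5.
- Deaths all ranked shortest, the extreme form of counting death as end of stay: 0.5 − (a − b)/126.
- Standard error: sqrt(127/(12 × 63 × 63)) = 0.0516.
- At 4 v 2 deaths the shift is 2/126 = 0.016, or 0.3 SE. At 5 v 1 it is 4/126 = 0.032, or 0.6 SE.

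**Simulation of the two readings the text invites** (deaths excluded, or stay ending at death). None of these assumptions is in the SAP: lognormal stay rounded up to whole days, median 3 to 8 days, log-SD 0.5 to 0.9, in-hospital mortality 3% to 8% and equal in both arms, death time uniform within the stay, Wilcoxon-Mann-Whitney test.

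| Situation | Result |
|---|---|
| No effect, each reading alone | rejects in about 4% to 6% of trials |
| No effect, at least one of the two | rejects in 6% to 7% |
| Near 60% power | disagree on p<0.05 in about 6% to 13% |
| Near 80% power | disagree on p<0.05 in about 4% to 10% |

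If mortality were 8% v 2% with equal stays (assumed), the parameter averages 0.50 with deaths excluded and 0.49 with days to death counted as the stay.

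**Start point.** Suppose pre-randomisation days are independent of the later stay and have an SD q times as large. The noncentrality is then divided by sqrt(1 + q²). From 80% power, q = 0.2 gives 78% and q = 0.5 gives 71% (q is assumed). Randomisation balances these days in expectation, so no bias follows.

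**Weight.** With equal SDs at both times and correlation ρ, the variance of the ANCOVA estimate divided by that of the change score is (1 + ρ)/2. At ρ = 0.90 this is 0.95, and at ρ = 0.98 it is 0.99. Square roots of 0.975 and 0.995 mean a confidence interval 2.5% to 0.5% narrower (ρ is assumed).

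**The case against.** **The table only summarises an SOP.** It is introduced that way, the definition cell reads like data-entry notes, and the span from randomisation to discharge recurs in other rows. Counting from randomisation is the natural reading. That stands, and it is why the start-point conflict is minor. Still, nothing in the row says that one cell prevails over the other.

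**The as-observed sentence may already exclude deaths.** This is a partial answer. The section covers secondary outcomes in general, but the sentence sits among questionnaire text. It does not say whether a stay ended by death is missing or observed.

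**The effect could be made to look larger.** A reader might add a third rule, deaths ranked as the longest stay. Disagreement then rises to 17% to 28% of trials near 60% power and 12% to 22% near 80%, and rejection by at least one rule under no effect to 7% to 9%. The SAP never suggests that rule, so those figures do not measure its ambiguity.

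**Baseline adjustment is a preference.** Largely so: the planned comparison is valid and the gain is small. A reader might extend the point to diuretic dose, but the documents do not support that. At an assumed correlation of 0.5, with the outcome SD twice the baseline SD, ANCOVA gains nothing over the change score. In one assumed scenario rank ANCOVA lowered power from 79% to 67%.

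**Baseline timing.** A reader might also infer that a baseline weight could be taken after drainage, or that the baseline dose is unclear. The SOP, which is not shown, may settle both, and the baseline table lists home diuretic dose separately. No finding is made on either.

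**Conclusion.** The point holds as a minor one. The index-stay row contradicts itself on when the stay starts, and the SAP has no rule for the roughly 6 in-hospital deaths it expects. The first fault costs some precision. The second leaves open a choice that would change the significance verdict in about 4% to 13% of trials when there is an effect to find. It lifts the chance of a false positive from about 5% to 6% to 7% only if the more favourable result is picked. These sizes rest on assumed stay distributions, equal mortality and 63 per arm. The weight point concerns precision alone and depends on a high assumed correlation.

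A reader might infer that the start-point conflict biases the comparison, that one of the two death readings is invalid under equal mortality, or that the main result is in doubt. None of these follows. Death is still captured by the primary outcome, by time to death, and by time to first readmission or death.

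**What to change.** 1. Count index stay from randomisation in both cells of the row, as the primary outcome does.
2. Fix one rule for in-hospital deaths before the data are seen, and do not count death as a short completed stay. Report in-hospital deaths per arm beside the result. Add one sensitivity analysis: deaths ranked as the longest stay, or time to discharge alive with death as a competing event. Ranking deaths longest mixes stay with death and costs power when mortality is equal (48% to 57% against 58% to 60% with deaths excluded, in the simulation), so it suits a sensitivity analysis better than the main one.
3. Analyse discharge weight by ANCOVA on baseline weight and the randomisation strata (anticoagulation, and site where numbers allow). Keep the planned test for diuretic dose. Report per arm how many lack a discharge weight or dose because they died.

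The cost is SAP wording and slightly more analysis work. No new data are needed, and the primary outcome and sample size do not change.
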